4.8.1.6 Supplementary Analyses of the Primary Efficacy Endpoint

Supplementary analyses will be performed using the same logistic regression model as the primary analysis (section 4.8.1.2) based on Stage I data using the full analysis set. These supplementary analyses provide additional insights for primary efficacy results. Treatment policy will be used to handle rescue medication use and treatment discontinuation, i.e., including all observed data collected after rescue medication administration and treatment discontinuation regardless of receipt of rescue therapy or treatment discontinuation.

The proportion of subjects that achieved CRR at Week 48 but not at Week 52 will be computed by randomized treatment group using the Full Analysis Data Set.

4.8.1.7 Handling Plan for Missing Data

4.8.1.7.1 Imputation if Missing a Single Lab Component within a Visit

The 24-hour UPCR and eGFR values will be used for the primary efficacy endpoint evaluation. No imputation will be performed for missing baseline values. If either the 24-hour UPCR or eGFR is missing at a single treatment visit,

- the missing 24-hour UPCR will be imputed using the observed spot UPCR from the same visit unless a 24-hour UPCR can be obtained from a recent unscheduled visit (e.g., within maximum 4-week period), then the 24-hour UPCR from this unscheduled visit will be used. Otherwise, the 24-hour UPCR will be imputed using Last Observation Carried Forward (LOCF) of the most recent scheduled measurement of 24-hour UPCR if available or spot UPCR when 24-hour UPCR is unavailable.
- the missing eGFR will be imputed using LOCF.

4.8.1.7.2 Imputation for Missing Data

The intermittent missing data will be imputed using LOCF. Participants with missing outcomes due to early discontinuation from the study will be considered as non-responders.

4.8.2 Secondary Efficacy Endpoints and Analyses

4.8.2.1 Secondary Efficacy Endpoints and Estimands

The estimand for the binary secondary efficacy endpoints is defined as follows, using composite variable strategy to address intercurrent events.

1. Population:

- a. ORR: Participants in the Full Analysis Set.
- b. Sustained reduction of oral corticosteroids (OCS) dose: Participants in the Full Analysis Set whose Baseline OCS dose is greater than 2.5 mg/day prednisone equivalent (Appendix 1).

2. Variables (outcome measures):
 - a. ORR at Week 48 and sustained through Week 52 (ORR is defined as CRR or PRR). CRR was defined in primary endpoint. PRR is defined by meeting the following criteria:
 - i. $eGFR \geq 60 \text{ mL/min}/1.73\text{m}^2$ or no worse than 15% below baseline.
 - ii. Improvement in 24-hour UPCR:
 - For participants with a baseline UPCR $\leq 3.0 \text{ mg/mg}$: $< 1.0 \text{ mg/mg}$
 - For participants with a baseline UPCR $> 3.0 \text{ mg/mg}$: $> 50\%$ improvement from baseline and $\leq 3.0 \text{ mg/mg}$
 - iii. No use of restricted medication beyond the protocol allowed threshold before assessment.
 - iv. No discontinuation of study intervention.
- b. Response in sustained reduction of OCS dose, which is defined by meeting the following criteria:
 - i. Prednisone-equivalent dose $\leq 2.5 \text{ mg/day}$ by Week 24 and not exceeding this dose through Week 52.
 - ii. No use of restricted medication beyond the protocol allowed threshold before assessment.
 - iii. No discontinuation of study intervention.

3. Intercurrent event:
 - a. Rescue medications: Captured in the variable definition.
 - b. Treatment discontinuation: Captured in the variable definition.
4. Population-level summary: Difference in proportions of responders between the daxdilimab group and placebo group.

The estimand of change from baseline in eGFR at Week 52 is defined as follows, using hypothetical strategy to address intercurrent event of rescue medications by assuming data is missing as missing at random (MAR) after rescue medication and treatment policy strategy to address intercurrent event of treatment discontinuation by continue taking measures regardless of treatment discontinuation.

1. Population: Participants in the Full Analysis Set.

2. Variable (outcome measure): Change from baseline in eGFR at Week 52.
The baseline values of eGFR are defined in Section 4.8.1.2
3. Intercurrent event:
 - a. Rescue medications: The data collected after administration of the rescue medications will be treated as missing and be imputed based on assumption of MAR. That is the participants have followed the trend of his or her own treatment group
 - b. Treatment discontinuation: Participants who discontinue study intervention will be asked to come to scheduled evaluations until the end of study. The data collected after discontinuation of study intervention will be included in the analysis
4. The population-level summary: Mean difference of change from baseline on eGFR between the daxdilimab group and placebo group.

4.8.2.2 Secondary Efficacy Analyses

The secondary efficacy analyses will be based on the FAS. No adjustment for multiplicity will be performed.

- 1) ORR will be analyzed using a logistic regression model with treatment, baseline eGFR value and baseline UPCR value included in the model. Response in sustained reduction of OCS dose will be analyzed similarly using a logistic regression model with treatment, randomization stratification factors and baseline OCS dose included in the model. The difference in proportions of responders of daxdilimab vs placebo will be estimated together with its associated 2-sided 90% confidence interval (CI).
- 2) Change from baseline in eGFR will be analyzed using mixed models for repeated measures (MMRM) with treatment, visit, visit by treatment interaction, randomization stratification factor (UPCR only), and baseline eGFR value included in the model. The normality test will be performed on change from baseline in eGFR. If it fails for normal assumption, the data of change from baseline in eGFR will be log-transformed. An unstructured covariance matrix will be used to model the correlations among repeated measurements within each participant. In case of convergence issues, another structure, for instance, a first-order autoregressive covariance matrix will be used. Covariance parameters will be estimated using restricted maximum likelihood method and Kenward-Roger approximation will be used to estimate denominator degrees of freedom for the tests of fixed effects. The treatment effect will be evaluated at Week 52 along with two-sided 90% CI will be reported.
- 3) A bar chart will be provided showing the proportion of participants meeting the criteria for ORR and individual components of ORR at [REDACTED] [REDACTED] by treatment groups. A line plot up to [REDACTED] will also be produced by treatment groups.

[figure not shown]
- 4) The trajectory of eGFR over time will be visually presented by plotting the mean eGFR at each time point by treatment groups.

[figure not shown]

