				■			■			■					■
Pregnancy (urine) test ^g	X	X	X	X	X	X	X	X	X	X	X	X	X	X	X
	■	■	■	■	■	■	■	■	■	■	■	■	■	■	■
24-hour UPCR ^h	X				X			X			X			X	X
Routine chemistry ⁱ	X	X	X	X	X	X	X	X	X	X	X	X	X	X	X
Hematology (CBC with differential)	X				X			X			X			X	X
Lipid profile ^j	X							X							X
Urinalysis ^k	X				X			X			X			X	X
	■				■			■			■			■	■
	■				■			■			■			■	■
	■				■			■			■			■	■
	■				■			■			■			■	■

Table 3 First Year Treatment Procedures and Assessments

Period	Treatment Period																					
Study Week																						
Study Day																						
Visit Window (\pm Days)	-	3	3	5	5	5	5	5	7	7	7	7	7	7	7							
Visit Number	2	3	4	5	6	7	8	9	10	11	12	13	14	15	16							
███████████	█		█		█			█			█			█	█							
███████████	█		█					█						█	█							
CCI ██████████	█		█		█			█			█			█	█							
███████████	█		█					█							█							
Daxdilimab PK (serum) ^m	X	X	X	X	X	X	X	X			X			X	X							
Daxdilimab ADA ⁿ	X		X		X			X			X			X	X							
███████████	█		█		█			█			█			█	█							
███████████	█	█						█						█	█							
███████████	█							█							█							
Screening biopsy sample shipment for adjudication ^p	X																					
███████████	█																					
Study treatment administration																						
Local injection site assessment																						
MMF/MPA/OCS dispensing ^r	X	X	X	X	X	X	X	X	X	X	X	X	X	X	X							
IV methylprednisolone administration ^s	X																					
Oral corticosteroid reduction (tapering)		X	X	X	X	X	X		X	X	X	X										
Concomitant medications ^t	◀	Continuous													▶							
AEs, SAEs, and/or AESIs ^u	◀	Continuous													▶							

ADA = antidrug antibody; AE = adverse event; AESI = AE of special interest; CBC = complete blood count; ECG = electrocardiogram; ██████████ IP = investigational product; MMF = mycophenolate mofetil; MPA = mycophenolic acid; mSFI = modified Systemic Lupus International Collaborating Clinics/American College of Rheumatology; ██████████ OCS = oral corticosteroids; ██████████ PK = pharmacokinetics;

███████████ SAE = serious AE; ██████████ X = to be performed.
 SLICC/ACR = Systemic Lupus International Collaborating Clinics/American College of Rheumatology; ██████████

^a Participant eligibility (based on Screening assessments, including non-laboratory-based assessments at Baseline [Day 1] as per the inclusion and exclusion criteria) must be checked again on Day 1 prior to Randomization.

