4.8.1.4 Control of Type I Error

1. The type I error rate will be controlled at a 0.1 level (2-sided) for the primary efficacy analysis using a fixed sequence testing procedure. The primary endpoint will be tested for daxdilimab [REDACTED] mg compared with placebo.
2. If p-value is \leq 0.1 in step 1, the primary endpoint will be tested for daxdilimab [REDACTED] mg compared with placebo. If step 1 test is not significant, the test for Daxdilimab [REDACTED] mg will not be performed.

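### The eGFR MMRM's fallback covariance is left open, and its only named example, AR(1), would understate the Week 52 standard error if variance grows over the year

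*SAP*

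**What the plan says.** SAP 4.8.2.2 item 2 analyses change from baseline in eGFR with an MMRM whose mean model has "treatment, visit, visit by treatment interaction, randomization stratification factor (UPCR only), and baseline eGFR value included in the model". The first-choice covariance is unstructured: "An unstructured covariance matrix will be used to model the correlations among repeated measurements within each participant". If that fails, "In case of convergence issues, another structure, for instance, a first-order autoregressive covariance matrix will be used". Estimation is by restricted maximum likelihood, and "Kenward-Roger approximation will be used to estimate denominator degrees of freedom for the tests of fixed effects". No empirical (sandwich) standard error is mentioned. The result reported is a single contrast: "The treatment effect will be evaluated at Week 52 along with two-sided 90% CI will be reported".

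On error control, SAP 4.8.2.2 says of the secondary analyses: "No adjustment for multiplicity will be performed". SAP 4.8.1.4 confines the 0.10 level to the primary endpoint: "The type I error rate will be controlled at a 0.1 level (2-sided) for the primary efficacy analysis using a fixed sequence testing procedure".

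In Protocol 1.3, Table 3, the row "Routine chemistry" is marked at every first-year treatment visit (Visits 2 to 16), so there are 14 post-baseline time points.

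**The concern.** A fallback is meant to remove discretion after the data are seen. This one leaves the choice open, and the one structure it offers is a poor match for the estimand. Standard AR(1) has two parameters: one variance shared by all visits, and one correlation that decays with visit order. It therefore estimates the Week 52 variance largely from the other 13 visits. If changes in eGFR are tighter early and more dispersed at one year, that pooled variance is too low for the one visit that is reported. Kenward-Roger corrects for small-sample uncertainty in the estimated covariance. It does not repair a structure that is wrong.

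At stake are the nominal p-value and the coverage of the 90% interval for a secondary renal-function endpoint.

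**Working it through.** **What can be reproduced.** The documents give no SD, standard error, power or error rate for the eGFR model. Their only checkable figure is primary-endpoint power (SAP 2.3): 70 per arm, 25% v 45%, two-sided 0.10. (0.20·√70 − 1.645·√(2·0.35·0.65)) / √(0.25·0.75 + 0.45·0.55) = (1.673 − 1.110)/0.660 = 0.855, so power is 80.4%. This agrees with the stated figure. The arm size of 70 is used below.

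**Inputs from the documents.** Three arms of 70, and 14 post-baseline visits. The week row of Table 3 is redacted. The 24-hour UPCR weeks (Protocol 8.1) and PK weeks (Protocol 8.4), matched to the visit columns, fit Weeks 2, 4, 8 and then every 4 weeks to 52. I assume eGFR is available at each chemistry visit and that all 14 visits enter the model. The unstructured matrix then has 14·15/2 = 105 parameters.

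**Check 1: direct formula.** With complete data the Week 52 contrast is close to a difference in Week 52 means, so to a close approximation

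- SE ratio (AR(1)/true) = root-mean-square SD over the 14 visits ÷ SD at Week 52
- actual level = 2·[1 − Φ(1.645 × SE ratio)]

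Assume the SD changes linearly from Week 2 to Week 52. Example, SD ratio 1.5: with Week 2 SD = 1, the mean squared SD over visits is 1.566, so the ratio is √1.566/1.5 = 0.834 and the level is 2·[1 − Φ(1.372)] = 17.0%.

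The last two columns come from simulating a homogeneous AR(1) fit under no treatment effect: 5,000 trials per cell, a mixed true correlation pattern, and no dropout or 20% random dropout. Monte Carlo error is about 0.4 to 0.6 points. Kenward-Roger was approximated by large-sample critical values, a minor difference at this size.

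| Week 52/Week 2 SD | SE ratio | Level, formula | Simulated, no dropout | Simulated, 20% dropout |
|---|---|---|---|---|
| 0.5 | 1.55 | 1.1% | – | – |
| 0.67 | 1.26 | 3.8% | 4.6% | 3.6% |
| 0.8 | 1.13 | 6.3% | – | – |
| 1.0 | 1.00 | 10.0% | 10.5% | 9.8% |
| 1.25 | 0.90 | 13.9% | 13.6% | – |
| 1.5 | 0.83 | 17.0% | 16.4% | 17.4% |
| 2.0 | 0.76 | 21.2% | 21.1% | – |

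When variances are equal, a wrong correlation alone does little: with a compound-symmetric truth and 20% dropout the simulated level was 10.5%.

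**Check 2: a random-slope model.** Assume a between-person eGFR SD of 28, within-person noise SD of 7, and slope SD b in mL/min/1.73m² per year. Given baseline, the variance at time t (years) is 784·(1 − 784/833) + b²t² + 49 = 46.1 + b²t² + 49. For b = 9, the Week 52 variance is 176.1, so the true SE is √(2·176.1/70) = 2.24. The mean of t² over the visits is 0.346, so the average variance is 46.1 + 81·0.346 + 49 = 123.2, which gives an SE of 1.88. A large-sample AR(1) likelihood fit gives:

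| Slope SD | Week 52/Week 2 SD | AR(1) SE v true SE | Level |
|---|---|---|---|
| 0 | 1.00 | equal | 10.0% |
| 6 | 1.17 | 1.76 v 1.94 | 13.6% |
| 9 | 1.36 | 1.88 v 2.24 | 16.7% |
| 12 | 1.58 | 2.05 v 2.61 | 19.7% |

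**Check 3: what repairs it.** In the 11 scenarios run 5,000 times, which include those with model-based levels of 16% to 21%, an empirical standard error brought the level to between 9.2% and 11.0%, even with AR(1) as the working structure. Letting variances differ by visit helps but is not enough alone. In the random-slope model (b = 6, 9, 12), large-sample model-based Week 52 SEs are still about 3%, 7% and 10% too small under heterogeneous AR(1), and about 4%, 7% and 11% too small under heterogeneous Toeplitz.

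**The case against.** Several points on the other side stand.

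- **AR(1) is only an example.** The SAP does not commit to it and does not say whether the variances are homogeneous. A reader might infer that homogeneous AR(1) is the fixed fallback; the wording does not support that. What remains is that the choice is open and no safer option is named.
- **The direction is not given.** A reader might infer that the interval is too narrow whenever the fallback is used. That holds only if Week 52 variance exceeds the average over visits. Growth is plausible for a change score, but the documents give no eGFR SD at any visit.
- **The trigger is not shown to be likely.** With complete data there are 210 × 14 = 2,940 records for 105 covariance parameters. Treating post-rescue values as missing (SAP 4.8.2.1) thins the later visits, but nothing gives a rate of non-convergence.
- **The trial's error rate is not at risk.** The 0.10 level is controlled only for the primary complete renal response tests, and the eGFR result is nominal.

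One could instead refit the unstructured model on fewer visits, such as Weeks 12, 24, 36, 48 and 52 (15 parameters). That discards nine of the 14 visits and any participant with no usable eGFR from Week 12 on, so it is a debatable exchange.

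**Conclusion.** The point holds in conditional form. If the unstructured fit fails, and a homogeneous AR(1) with model-based errors is chosen, and the variance of eGFR change grows over the year, then the Week 52 standard error is too small. For assumed SD ratios of about 1.2 to 2 it is about 9% to 24% too small, the nominal 10% level becomes about 13% to 21%, and coverage of the 90% interval falls to about 87% to 79%. Flat variance gives no error. At SD ratios of 0.8 to 0.5 the level falls to 6.3% to 1.1%, which is conservative.

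These sizes rest on assumed variance patterns and a visit grid inferred from other sections. Two separate variance models and the simulation agree on them. The consequence is limited to one secondary endpoint. The change is still worth making, because the sponsor cannot know the variance pattern in advance and a prespecified fallback should not depend on it.

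**What to change.** Replace the fallback sentence in SAP 4.8.2.2 item 2 with:

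> *If the unstructured model does not converge, the following will be tried in order, keeping all visits: heterogeneous Toeplitz, then heterogeneous first-order autoregressive. For any structured matrix, empirical (sandwich) standard errors will be used, with between-within degrees of freedom in place of Kenward-Roger.*

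The empirical standard error is the essential part, as Check 3 shows. The heterogeneous structures keep the working model closer to the data, which also matters for the estimate when visits are missing. The cost is one sentence before unblinding. Kenward-Roger is given up in the fallback only, and sandwich errors are slightly more variable at about 70 per arm.

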4.8.2.3 Supplementary Analyses of the Secondary Efficacy Endpoints

Supplementary analyses using the same models as described in section [4.8.2.2](#) for each secondary endpoint will be performed based on Stage I data using the full analysis set. These supplementary analyses provide additional insights for the secondary efficacy results. Treatment policy will be used to address intercurrent events of rescue medication administration and treatment discontinuation, i.e., including all observed data collected after rescue medications administration and after discontinuation of treatment.

4.8.3.1.7 SDI

The Systemic Lupus International Collaborating Clinics/American College of Rheumatology Damage Index (SDI) has been developed to assess irreversible damage in SLE participants independently of its cause (ie, included damage due to SLE activity,

SLE-related scarring, therapy, comorbidities) but occurring after disease onset. Damage, ie, irreversible impairment since onset of SLE, is usually defined as a clinical feature that must be continuously present for at least 6 months to score. In addition, some irreversible events such as myocardial infarction or a cerebrovascular accident, score as damage on their occurrence. Briefly, damage is defined for 12 organ systems: peripheral vascular, ocular, neuropsychiatric, renal, pulmonary, cardiovascular, gastrointestinal, musculoskeletal, skin, endocrine (diabetes), gonadal, and malignancies. Damage over time can be stable or increase, theoretically to a maximum of 47 points ([Schwartz et al., 2009](#)).

The following SLICC/ACR SDI endpoints will be explored.

- Change from baseline in SDI over time.
- Proportion of participants with any SDI worsening (change from baseline > 0) over time.

[figure not shown]

[figure not shown]
[REDACTED]

[REDACTED]

[REDACTED]

[REDACTED]

4.9 Safety Analyses

4.9.1 Adverse Events

Safety analyses will be based on the actual treatment received and will be performed on the Safety Analysis Set, Stage II Analysis Set or Any Daxdilimab Set according to the study period being examined. All safety data will be provided in patient listings by treatment group.

No formal hypothesis is planned. In general, if an adverse event (AE) onset is on or after the first dose of trial intervention, the AE will be considered as a treatment-emergent adverse event (TEAE). Otherwise, the AE will be considered as a non-TEAE. Safety data will be presented separately for different study periods as defined in Table 5. In addition, the total number of participants with missed doses and reasons for missing (COVID-19 related or others) will be summarized by treatment group and overall.

Table 5 TEAEs for Different Study Periods

Study Period	Inclusion of TEAEs for Summary
Stage I (Safety Analysis Set)	Include AEs with an onset on or after the first dose of trial intervention in Stage I treatment period up to the time prior to the first dose of daxdilimab in Stage II treatment period ([REDACTED]) for participants who were dosed during the Stage II treatment period, and AEs with an onset on or after the first dose of trial intervention in Stage I treatment for participants not dosed in Stage II treatment.
Stage II (Stage II Analysis Set)	Include AEs with an onset on or after the first dose of daxdilimab in Stage II treatment period ([REDACTED]).

Table 5 TEAEs for Different Study Periods

Study Period	Inclusion of TEAEs for Summary
Any Daxdilimab Exposure (Any Daxdilimab Analysis Set)	Include AEs with onset on or after the first daxdilimab dose (either during Stage I or Stage II treatment period)

All AEs and TEAEs will be coded using the most recent version of MedDRA, and will be summarized by SOC and PT overall, by severity and by relationship to treatment. Participants having multiple AEs within a category (eg, overall, SOC, PT) will be counted once in that category. Specific AEs will be counted once for each participant for calculating rates, but all events will be presented in participant listings. In addition, for severity/relationship tables, if the same AE occurs multiple times within a particular participant, the highest severity/most related event within a category and level of causality will be reported.

SAEs and TEAEs will be summarized descriptively by treatment group and overall. Percentages will be based on the number of treated participants in the safety set within a treatment group and overall. Tables will be sorted by descending frequency of SOC and by descending frequency of PT within an SOC. Specific AEs will be counted once for each participant for calculating rates, but all events will be presented in participant listings. Listings will be provided for all TEAEs and non-treatment-emergent AEs.

TESAEs will be summarized by serious adverse event (SAE) criteria as well.

The following definitions will be used for AEs:

- **Treatment-emergent adverse event (TEAE):** Any AE with an onset on or after the first dose of study intervention
- **Treatment-emergent SAE (TESAE):** A TEAE that is serious. The details are referenced in Section 8.3.1.3 of protocol

A table will show the number and percentage of participants with at least one event in any of the following categories overall as well as by SOC and PT:

- TEAE
- Treatment-emergent serious adverse event (TESAE)
- TEAE resulting in death
- CTCAE Grade 3 or higher TEAE
- TEAE leading to discontinuation of trial intervention
- Serious and/or grade 3 or higher TEAE
- Trial intervention related TEAE
- Trial intervention related TESAE

An AE of special interest (AESI) is an AE of scientific and medical interest specific to the understanding of the trial intervention and may require close monitoring and collection of additional information by the Investigator. AESIs for this protocol include:

- Hypersensitivity reaction, including anaphylaxis
- Severe viral infection/reactivation (CTCAE v5.0 Grade 3 or higher)
- Opportunistic infection as listed in protocol appendix 2
- Malignancy (except non-melanoma skin cancer)

Treatment emergent AESIs will be summarized by type of AESI as listed above as well as SOC and PT.

Anaphylaxis will be searched using the NIAID (Sampson et al. 2006). The hypersensitivity reactions will be defined using Standardized MedDRA Queries (SMQ): hypersensitivity (narrow). Severe viral infection will be searched using MedDRA HLGT of Viral infectious disorders. Viral reactivation will be searched using MedDRA HLT Hepatic viral infection. Malignancy will be searched using MedDRA SMQ Malignant tumors. All will be described in the Statistical Programming Plan (SPP).

Individual listings will be presented for AEs leading to study treatment discontinuation, AEs leading to withdrawal from the study, AEs starting during administration of study intervention, and fatal AEs.

